10.1.4 Pharmacokinetic analysis set

The pharmacokinetic analysis set (PAS) consists of all patients who have at least one blood sample providing evaluable drug concentration data. The PAS will be used for summaries of PK data (Tables and Figures) as well as for listings of derived parameters.

Note: Patients will be removed from the estimation of certain PK parameters on an individual basis depending on the number of available blood samples. These patients will be identified at the time of the analyses and prior database lock.

10.2 Patient demographics/other baseline characteristics

Demographic and other baseline data including age, gender, height, weight, medical condition, disease characteristics, etc. will be summarized descriptively for all patients in the FAS. Categorical data will be presented as frequencies and percentages. For continuous data, mean, standard deviation, median, 25th and 75th percentiles, minimum, and maximum will be presented.

10.3 Treatments (study treatment, concomitant therapies, compliance)

10.3.1 Study treatment

The actual dose and duration in days of LEE011 treatment as well as the dose intensity (computed as the ratio of actual dose received and actual duration) and the relative dose intensity (computed as the ratio of dose intensity and planned dose received/planned duration), will be listed and summarized.

The summary data will be presented for each treatment cycle individually, as well as for all study days as a single category.

10.3.2 Concomitant therapies

Concomitant medications and significant non-drug therapies prior to and after the start of the study drug treatment will be listed by patient and summarized by ATC term by means of contingency tables.

10.3.3 Compliance

Compliance to the protocol will be assessed by the number and proportion of patients with protocol deviations. These will be identified prior to database lock and will be listed and summarized.

10.4 Primary objective

[figure not shown]
The primary objective of the study is to estimate the MTD and/or the RDE of LEE011 when administered as a single agent orally in patients. The corresponding primary analysis method is an adaptive BLRM guided by the EWOC principle ([Neuenschwander et al 2008](#)).

10.4.1 Variable

The primary endpoint is the incidence of DLTs in cycle 1. Estimation of the MTD of the treatment will be based upon the estimation of the probability of DLT in Cycle 1 for patients in the DDS. This probability is estimated by the model in [Section 10.4.2](#).

10.4.2 Statistical hypothesis, model, and method of analysis

An adaptive BLRM with 2 parameters, guided by the EWOC principle, will be used to make dose recommendations and estimate the MTD/ RDE during the study. The use of Bayesian response adaptive models for Phase I studies has been advocated by the EMEA guideline on

small populations 2006 and by [Rogatko et al \(2007\)](#) and is one of the key elements of the FDA's Critical Path Initiative.

The adaptive BLRM model will be fitted on the dose-limiting data (i.e. absence or presence of DLT) accumulated in cycle 1 throughout the dose escalation part (and possibly during the dose expansion part), for modeling the dose-DLT relationship of LEE011.

The DLT relationship in the escalation part of the study will be described by the following Bayesian logistic regression model:

$$\text{logit}(\pi_{(d)}) = \log(\alpha) + \beta \log(d/d^*), \quad \alpha > 0, \beta > 0$$

where $\text{logit}(\pi_{(d)}) = \ln(\pi_{(d)}/(1-\pi_{(d)}))$, and $\pi_{(d)}$ is the probability of a DLT at dose d . Doses are rescaled as d/d^* with reference dose of $d^* = 580 \text{ mg/m}^2$. As a consequence α is equal to the odds of the probability of toxicity at d^* . Note that for a dose equal to zero, the probability of toxicity is zero.

If a different dosing schedule will be considered, a Bayesian Meta-analytic approach will be used to take into account historical data collected for the initially planned schedule in the actual study, in order to derive an informative prior estimation of the dose-toxicity relationship for the new dosing regimen. This informative prior will be combined with DLT data for the new dosing regimen using a 2-parameter BLRM.

For further details of the statistical model including specification of prior distribution for the BLRM parameters, implementation and results under a variety of data scenarios please refer to [Appendix 7](#).

Dose recommendation

[figure not shown]
Dose escalation

After each cohort of patients, the posterior distributions for the probabilities of DLT rates at different dose levels are obtained. The results of this analysis are summarized in terms of the estimated probabilities that the true rate of DLT at each dose-level will lie within each of the following intervals:

- [0, 0.166) under-dosing
- [0.166, 0.333) targeted toxicity
- [0.333, 1.00] excessive toxicity

The overdose control criterion mandates that any dose of LEE011 for which the DLT rate has more than a 25% chance of being excessively toxic, i.e. exceeding 0.333, will not be considered for the next dose cohort. The final estimate of the MTD/RDE before the start of the expansion will also satisfy this condition.

Note that the dose that maximizes the posterior probability of targeted toxicity is the best estimate of the MTD, but it may not be an admissible dose according to the overdose criterion if the amount of data is insufficient. If vague prior information is used for the probabilities of DLT, in the early stages of the study this escalation procedure will reflect a conservative strategy.

Details of the criteria for dose escalation and the determination of the MTD are provided in [Section 6.2.2](#).

Dose expansion

Upon completion of the first cycle of treatment for at least 10 patients within the dose expansion part, if the observed DLT rate exceeds 33%, the BLRM will be re-run to confirm that the estimated MTD/RDE still satisfies the overdose criterion. If the dose fails to satisfy the criterion a change to the dose under study may be made according to the Bayesian model recommendation, after review of the clinical data.

Listing/ summary of DLTs

DLTs will be listed and their incidence summarized by primary system organ class, worst grade based on the CTCAE version 4.03, type of adverse event, and by treatment group. The dose-determining set will be used for these summaries.

10.4.3 Handling of missing values/censoring/discontinuations

Continuing events (e.g. AEs, concomitant medication, etc.) will be summarized using the data cut-off date as the date of completion, with an indication within listings that the event is continuing. For patients who discontinue the study with ongoing events, the discontinuation date will be used as the completion date of the event with the appropriate censoring as described in the above paragraph.

The reason for discontinuation from study will be summarized and listed, along with dates of first and last study drug treatment, duration of exposure to study drug treatment and date of discontinuation for each patient.

Other missing data will simply be noted as missing on appropriate tables/listings.

10.4.4 Supportive analyses

Supportive analyses may be performed to incorporate later cycle DLT data to provide additional guidance for dose escalation within the escalation part of the study.

Additional exploratory and supportive analyses will be conducted if appropriate and defined in the reporting and analysis plan (RAP).

10.5 Secondary objectives

Refer to [Section 3](#) for secondary objectives of dose escalation part and dose expansion part.

10.5.1 Population and grouping for the analyses

For all safety analyses, the safety population will be used. All other secondary analyses will use the population specified in the relevant section below. All listings and tables will be presented by treatment group (or study arm for efficacy analysis in the expansion part with patients classified to treatment group as described in [Section 10](#).

10.5.2 Safety evaluation

10.5.2.1 Analysis set and grouping for the analyses

The overall observation period will be divided into three mutually exclusive segments:

1. Pre-treatment period: from day of patient's informed consent to the day before first dose of study medication.
2. On-treatment period: from day of first dose of study medication to 30 days after last dose of study medication.
3. Post-treatment period: starting at day 31 after last dose of study medication.

10.5.2.2 Adverse events (AEs)

All adverse events recorded during the study will be summarized. The incidence of treatment-emergent adverse events (new or worsening from baseline) will be summarized by primary system organ class, severity based on the CTCAE version 4.03, type of adverse event, and relationship to the study drug by treatment group. Deaths reportable as SAEs and non-fatal serious adverse events will be listed by patient and tabulated by primary system organ class, type of adverse event, and by treatment group.

Any other information collected (e.g. start/end dates and duration of adverse event, severity or relatedness to study medication) will be listed as appropriate.

10.5.2.3 Laboratory abnormalities

All laboratory values will be converted into SI units, as appropriate, and the severity grade calculated using CTCAE, version 4.03. Parameters for which a grading does not exist will be classified into low/normal/high group by means of laboratory normal ranges.

[figure not shown]
For each laboratory test (e.g. hematology, biochemistry, etc.) a listing of laboratory values will be provided by laboratory parameter, patient and treatment group. The frequency of notable lab abnormalities will be displayed by parameter, cycle and treatment group. Similarly, the frequency of all laboratory abnormalities will be displayed by parameter, worst CTCAE version 4.03 grade experienced and treatment group. A separate listing will display notable laboratory abnormalities (i.e., newly occurring CTC grade 3 or 4 laboratory toxicities).

Laboratory data will be summarized by presenting grade shift tables for those parameters for which CTCAE version 4.03 allows classification. All remaining data will be summarized by presenting shift tables based on normal ranges.

Laboratory data will also be displayed by presenting summary statistics of raw data and change from baseline values (means, medians, standard deviations, ranges).

10.5.2.4 Electrocardiograms

Data from electrocardiograms will be listed, notable values will be flagged and any other information collected will be listed as appropriate. Furthermore, combined QTc values from the triplicate ECGs will be averaged to provide a single value for each patient and to be used in the summary tables.

Change from baseline in QT intervals by treatment will be summarized for each visit. Moreover change from baseline in all ECG parameters for the worst change from baseline will be summarized. The frequency and percentage of patients with notable ECGs and newly occurring qualitative ECG abnormalities will be tabulated by treatment group and mutually exclusive categories of QTcF, QTcB, QT, HR, PR, QRS (see [Table 10-1](#)).

In the listings of baseline cardiac imaging results subjects with a notable post-dose QTc abnormality will be identified.

Table 10-1 ECG parameters and abnormal values

ECG Parameter	Abnormal values
QT, QTcF and QTcB	New absolute values >450, >480 and >500 Changes from baseline >30 and >60
HR	Decrease from baseline >25% and to a HR < 50 Increase from baseline >25% and to a HR > 100
PR	Increase from baseline >25% and to a value >200
QRS	Increase from baseline >25% and to a value >110

QT or QTc values will also be also considered notable when >450 msec, >480 msec and > 500 msec. They will be flagged as such in listings.

The difference between baseline and maximum post-QTcF values will also be summarized. Post-baseline values will also be presented in the following categories: an increase from baseline of > 30 msec or > 60 msec, or new absolute values > 450 msec, > 480 msec, or > 500 msec. A frequency table for such categories will be summarized by treatment.

A listing of QT prolonging concomitant medications will be produced.

Additional outputs and details will be fully specified in the RAP.

10.5.2.5 Other safety data

[figure not shown]
Data from other tests (e.g., vital signs) will be listed, notable values will be flagged, and any other information collected will be listed as appropriate. Any statistical tests performed to explore the data will be used only to highlight any interesting comparisons that may warrant further consideration.

10.5.2.6 Supportive analyses for secondary objectives

Additional exploratory and supportive analysis will be conducted if necessary and specified in the RAP.

10.5.3 Tolerability

Tolerability of study drug LEE011 will be assessed by summarizing the number of dose interruptions and dose reductions. Reasons for dose interruption and dose reductions will be listed by patient and summarized. Cumulative dose, dose intensity and relative dose intensity of LEE011 will be listed by patient and summarized. Categories for relative dose intensity of LEE011 will be specified as < 0.5, ≥ 0.5 - < 0.75, ≥ 0.75- < 0.9, ≥ 0.9-< 1.1, ≥1.1. The number and proportion of patients within each category will be presented.

10.5.4 Efficacy evaluation

Assessment of preliminary efficacy for all patients will be based on RECIST v1.1 ([Appendix 1](#)). In addition, patients with primary CNS tumors (including MRT) will have response assessment per RANO criteria ([Appendix 3](#)) whenever possible. Disease response in Neuroblastoma patients will additionally be assessed per INRC ([Appendix 2](#)).

TTP and DOR per RECIST v1.1 will be presented descriptively for the neuroblastoma and the MRT arms in the expansion phase using a Kaplan-Meier curve. Summary statistics from the Kaplan-Meier distribution will be determined, including the median and estimates at 4 and 8 months, for TTP and DOR respectively. These statistics will be provided as point estimates with 95% confidence intervals.

ORR as per RECIST v1.1 will be presented at the MTD/RDE as point estimate and corresponding 95% exact confidence interval according to Clopper-Pearson for the neuroblastoma and the MRT population separately.

The same analysis will also be presented as per RANO in MRT patients and as per INRC in Neuroblastoma patients.

Moreover, preliminary efficacy response as per RECIST 1.1 will be listed for all patients as well as preliminary efficacy response per RANO and INRC for patients with Primary CNS and with Neuroblastoma, respectively.

Any other additional analysis will be fully specified in the RAP.

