2.3 Rationale for dose and regimen selection

The MTD of LEE011 for the 3 weeks on/1 week off schedule is 900 mg. The RDE in adults will most likely be 600 mg on the same regimen. The dose from the adult Phase 1 study that will be used to calculate the starting dose in children is 600 mg/d. This is based upon review of the safety, tolerability, and PK observed at this dose level and higher. At the 600 mg/d dose in adults, LEE011 was well tolerated with an acceptable safety profile. At this dose, systemic exposures corresponding to efficacy in preclinical models was observed. On target toxicity, neutropenia, was seen but not dose-limiting. Therefore, using the 600 mg/d dose from the adult study for calculating the starting dose in children offers a high probability of beginning at an active dose and a low probability of excessive toxicity.

The first cohort of children in this trial will be treated with a dose of 280 mg/m²/d, which is 80% of the current well tolerated dose (600 mg/d) in the ongoing adult study [CLEE011X2101] divided by the average adult body surface area (BSA) of 1.72 m². Refer to Section 6.2.1 for details.

In adults, LEE011 is dosed once daily orally, and the T_{1/2}, acc ranges from 24.2 to 40 hours. This supports once daily dosing in children. LEE011 will be dosed once a day for 21 consecutive days followed by a 7-day planned break as part of each 28-day cycle of treatment consistent with the regimen used in [CLEE011X2101].

3 Objectives and endpoints

Objectives and related endpoints are described in Table 3-1 below.

[figure not shown]

Table 3-1 Objectives and related endpoints

Objective	Endpoint	Analysis
Primary		
Determine the MTD and/or RDE of LEE011	Incidence rate of DLTs in Cycle 1	Refer to Section 10.4 .
Secondary		
(1) Characterize the safety and tolerability of LEE011	(1) AEs and serious adverse events (SAEs), changes in laboratory values and electrocardiograms (ECGs).	Refer to Section 10.5 .
(2) Characterize the PK of LEE011 and any clinically significant metabolites that may be identified	(2) Plasma concentration time profiles of LEE011, PK parameters, including but not limited to AUCtau, Cmax, Tmax, CL/F, accumulation ratio (Racc), and T1/2,acc	
(3) Assess the anti-tumor activity of LEE011	(3) Overall response rate (ORR), duration of response (DOR), and time to progression (TTP) per RECIST 1.1. In addition, for neuroblastoma, response by INRC. In addition, for primary CNS tumors, response by RANO Criteria.	
Exploratory		

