4.1 Description of study design

This is a phase 1, multi-center, open-label study, with a dose escalation part followed by an expansion part. Eligible patients aged 12 months to 21 years old whose tumor has progressed following standard therapy, or for which no standard, effective therapy exists will be enrolled in the study. LEE011 will be administered orally, once daily for 21 days followed by a 1 week break (28-day cycle) at the starting dose of 280 mg/m²/d.. For the purpose of scheduling assessments and establishing the MTD/RDE, a cycle is defined as 28 days in length.

During the dose escalation part, 3-6 newly enrolled patients in successive cohorts will receive increasing doses of LEE011 with the dosing schedule specified above. A BLRM using the EWOC principle will be used to guide dose escalation. During the course of dose escalation, additional patients may be enrolled to previously tested lower dose levels that have been assessed as safe and well-tolerated if there is no slot available in the current cohort under testing. It is expected that approximately 10 patients may be enrolled and treated within this context. In all, it is anticipated that approximately 28 patients will be treated during the escalation part.

Once the MTD/RDE has been determined, the expansion part will begin to better characterize the safety, tolerability and PK profile of LEE011, as well as assess preliminary antitumor activity of LEE011. During the expansion part of the study LEE011 will be dosed at the MTD, or at a lower RDE, if the available data suggest that the MTD is not appropriate for multiple cycles of therapy. This part will include 2 arms, one restricted to neuroblastoma patients and the second to MRT patients with either CNS or extra-CNS primary. A minimum of 8 patients each will be required for CNS and extra-CNS primary MRT. Enrollment will proceed in parallel. Patients enrolled during the expansion part of the study are required to have measurable disease. Approximately 18 patients will be treated in each arm, for a total of approximately 36 patients in the expansion part.

[figure not shown]

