7.2 Assessment types

7.2.1 Efficacy assessments

[figure not shown]
All patients will have disease response assessment per RECIST v1.1 ([Appendix 1](#)). Patients with primary CNS tumors (including MRT) will have response assessment per RANO criteria ([Appendix 3](#)) whenever possible, in addition to RECIST. Disease response in neuroblastoma patients will be assessed per INRC ([Appendix 2](#)) whenever possible in addition to RECIST. Response assessments for patients with MIBG-positive disease and bone marrow-positive disease will also be done when applicable, per standard institutional practice. Disease response and progression will be determined locally by the investigator. All imaging procedures at screening must be completed within 28 days of the first dose of LEE011.

For patients with primary CNS (including MRT), the method of measurement should follow the neuro-oncology criteria of tumor response using 2-dimensional and volumetric measurements (if available) on gadolinium chelate-enhanced brain tumor magnetic resonance imaging (Gd-MRI) ([Appendix 3](#)). All Gd-MRIs (standard brain tumor magnetic resonance imaging [MRI] including both pre-contrast and post-contrast images using a Gadolinium (Gd) chelate as the contrast agent) should be performed when the patient is on a non-increasing dose of corticosteroids for at least 7 days.

For patients with non-CNS tumors, the method of measurement should follow standard practice (ie, computed tomography [CT] or MRI scans) and response will be assessed using Response Evaluation Criteria in Solid Tumors (RECIST) version 1.1 ([Appendix 1](#)). Patients with neuroblastoma will undergo MIBG scanning, and bone marrow aspirate and/or biopsy for presence of disease per standard institutional practice at screening. The use of ¹²³I for MIBG imaging is recommended for all scans. MIBG scans and bone marrow aspirates and/or biopsies should be performed within 28 days of the first dose of LEE011. Visible skin lesions and easily palpable subcutaneous tumors may be measured by physical examination using a ruler or calipers. Ultrasound should not be used to measure tumor lesions.

Each lesion that is measured at baseline (screening), must be measured by the same method throughout the study so that the comparison is consistent.

Antitumor activity in patients with non-measurable disease will only be noted.

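### The RANO response rate is planned for MRT patients without restriction, although only primary CNS tumors are assessed by RANO; the denominator should be limited to primary CNS MRT

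*Protocol*

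**What the plan says.** **Who is in the RANO rate.** Protocol Section 10.5.4 plans the RECIST ORR at the MTD/RDE as a point estimate with a "95% exact confidence interval according to Clopper-Pearson for the neuroblastoma and the MRT population separately". The next sentence extends this to the other criteria: "The same analysis will also be presented as per RANO in MRT patients and as per INRC in Neuroblastoma patients". No CNS restriction is attached to the RANO part.

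**Who is assessed by RANO.** Section 7.2.1: "Patients with primary CNS tumors (including MRT) will have response assessment per RANO criteria". The opening paragraph of Section 10.5.4 repeats this: "patients with primary CNS tumors (including MRT) will have response assessment per RANO criteria". Both add that it is done where feasible. The endpoint in Table 3-1 reads: "In addition, for primary CNS tumors, response by RANO Criteria".

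**Who is in the RANO listing.** The last listing sentence of Section 10.5.4 covers "preliminary efficacy response per RANO and INRC for patients with Primary CNS and with Neuroblastoma, respectively".

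**Who is in the MRT arm.** Section 4.1 describes two expansion arms, "the second to MRT patients with either CNS or extra-CNS primary", and adds: "A minimum of 8 patients each will be required for CNS and extra-CNS primary MRT". About 18 patients are planned per arm. Section 10.8 counts MRT patients treated at the MTD/RDE during escalation towards that number.

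**Which set applies.** Section 10.1.1 makes the FAS, all patients with at least one dose, the default. Section 10.5.4 names no other set.

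**The concern.** Within Section 10.5.4 the RANO rate and the RANO listing are written for different patients. The listing follows the endpoint definition (primary CNS). The rate follows the RECIST population (all MRT). An extra-CNS MRT patient has no planned RANO assessment and so cannot be a RANO responder, whatever the drug does. Putting such patients in the denominator pulls the rate down for a reason unrelated to activity, and the exact interval is computed on more patients than carry information.

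Activity in CNS disease is a question of its own here. Section 2.1 notes that the drug did not cross the blood-brain barrier preclinically and argues that primary CNS MRT is still worth studying. A diluted rate with too low an upper limit could be read as ruling out activity in CNS disease when the data do not do so.

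**Working it through.** **The plan's own figures.** No RANO rate or precision is stated. The only calculated figure in Section 10.8 is the 97% chance of seeing at least one adverse event of true rate 10% in 36 patients: 1 − 0.9^36 = 0.977, which agrees within a point. The counts also agree: 2 × 18 = 36 and 28 + 36 = 64.

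**Inputs for the RANO rate.**
- MRT arm: about 18 (Section 4.1).
- At least 8 CNS and at least 8 extra-CNS (Section 4.1), so CNS patients number 8 to 18 − 8 = 10.
- Denominator read literally: all treated MRT patients at the dose (Section 10.5.4 with the FAS default of Section 10.1.1).
- RANO responders can come only from the CNS patients (Table 3-1, Section 7.2.1).

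**Dilution factor.** With x responders, the all-MRT rate is x/18 and the CNS-only rate is x/n_CNS. Their ratio is n_CNS/18, whatever x is.

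| CNS patients of 18 | Ratio | A CNS rate of 30% (assumed) would show as |
|---|---|---|
| 8 | 8/18 = 44% | 13.3% |
| 9 | 9/18 = 50% | 15.0% |
| 10 | 10/18 = 56% | 16.7% |

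The ratio is also a ceiling: if every CNS patient responded, the reported rate would still be only 44% to 56%.

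**Effect on the exact interval.** Clopper-Pearson limits are the 2.5% quantile of Beta(x, n − x + 1) and the 97.5% quantile of Beta(x + 1, n − x), with lower limit 0 when x = 0. The responder counts are assumptions for illustration.

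| Denominator | 3 responders | 0 responders, upper limit |
|---|---|---|
| All MRT, n = 18 | 16.7% (3.6% to 41.4%) | 18.5% |
| CNS, n = 10 | 30.0% (6.7% to 65.2%) | 30.8% |
| CNS, n = 9 | 33.3% (7.5% to 70.1%) | 33.6% |
| CNS, n = 8 | 37.5% (8.5% to 75.5%) | 36.9% |

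With 3 responders the interval is 41.4 − 3.6 = 37.8 points wide on 18 patients, against 65.2 − 6.7 = 58.5 points on 10 and 75.5 − 8.5 = 67.0 points on 8.

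**What carries over to the halted trial.** SAP Section 4 says enrollment was halted and all analyses are for the escalation part only. The minimum of 8 per site belongs to the expansion part, and escalation has no such rule. If k of m MRT patients treated at the MTD/RDE in escalation had a CNS primary, the ratio is k/m. Neither number is given, so the ratio could lie anywhere from 0 to 1. It is 1, with no dilution, if all of them were CNS.

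**The case against.** The strongest reply is that the denominator is inferred. No sentence says that extra-CNS patients count as RANO non-responders. Section 10.5.4 begins by assigning RANO to primary CNS tumors, so one may read the rate as covering only MRT patients with a RANO assessment. Appendix 1, Section 3.1, says that patients with unknown best response may stay in the ORR denominator depending on the analysis population. That is permissive, and it concerns unknown assessments rather than a criterion that was never applied. This stands: the dilution follows from the literal sentence plus the FAS default and is not written out. It does not rescue the wording, because the listing sentence carries the CNS restriction and the rate sentence does not.

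Second, the protocol defers analysis detail to the Report and Analysis Plan, and SAP Section 2.2 refers to the primary CSR RAP Module 3 for analysis sets. That document is not available and may already restrict the rate. This also stands.

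Third, the stakes are limited. The rate is descriptive and supplementary, Section 10.9 gives no power for secondary variables, no dose rule uses it, and the patient listing would let a reader recover the CNS-only rate.

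Two stronger readings are tempting. A reader might infer that a reported RANO rate is in fact halved. The documents do not support that, because the 44% to 56% range needs a full expansion arm, which the SAP says is not analysed. A reader might also infer that CNS tumors other than MRT are wrongly left out. ORR is planned only for neuroblastoma and MRT, such tumors enter only in escalation, and their RANO responses are listed, so this is not a defect.

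**Conclusion.** The population stated for the RANO rate does not match the patients for whom RANO is assessed, and the sentence should be corrected. Under the literal reading with the FAS default, a full MRT arm of about 18 with at least 8 of each site would show 44% to 56% of the CNS-only rate, with an interval that is too narrow. That size rests on three assumptions: the planned arm size, the per-site minimum, and extra-CNS patients being kept in the denominator.

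For the trial as it ran, the size is unknown. It depends on the CNS/extra-CNS split among MRT patients treated at the MTD/RDE in escalation and on what the primary CSR RAP specified. The final CSR is not affected, since SAP Section 2.7 plans no secondary efficacy analysis there, and the SAP's list of changes does not mention the RANO population. The RECIST ORR for MRT is unaffected.

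**What to change.** Reword the RANO sentence in Section 10.5.4 along these lines: *Per RANO, the ORR at the MTD/RDE and its exact interval will be given for MRT patients with a primary CNS tumor; those without an evaluable RANO assessment count as non-responders, and the number assessed is shown alongside. Per INRC, the ORR will be given for neuroblastoma patients.* Keep the RECIST ORR for the whole MRT population.

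The clause on unassessed patients is needed because RANO is done only where feasible; limiting the rate to CNS primaries would otherwise leave the denominator open. The primary CSR RAP should be checked against this wording, and the RANO table should state its denominator.

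The cost is a few words, a smaller denominator and a wider interval, which reflects the information actually available. No extra data are needed.
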